### 9.0 Case Report Forms

Data collection for the current study will be conducted on traditional paper Case Report Forms (CRFs) that will be faxed to the Cato Research Data Collection Center or by using an Electronic Data Capture (EDC) system. The faxed CRFs will be reviewed and after verification the data will be collected in the data base. All edit checks will be programmed in the ORACLE Clinical platform and all study databases will be in ORACLE. The EDC system will be based on a paper CRF that will be approved by the sponsor and the principle investigators.

The study CRF or EDC interface will consist of the following sections:

- 1. Baseline / Screening: This will be used to enter all the data collected during the baseline / screening visit as described in Table 1 section 6.5.
- 2. Follow-Up Visits: These will be labeled as Visit 2 6 with the suggested time points of 3, 6, 12, 18 and 24 months indicated. However, as mentioned earlier this is the recommended schedule of visits and the investigators will be allowed to conduct the assessments according to their routine practice and judgment. Consequently the investigators will be instructed to use the individual CRF visit sections for visits that take place on time period that is nearest to the suggested time point. The date of the visit will be clearly indicated. The information

collected on these follow up visits are described in detail in Table 1 section 6.5.

- 3. Additional (Non Scheduled) Follow Up Visits: Blank CRF sections will be provided for the site investigators to enter the available data from additional visits.
- 4. End of Study: This will be a separate section of the CRF describing the final status of the patient in the study as "completed" or withdrawn. For patients that are withdrawn from the study the reason and date will be reported.

All CRF sections will contain the anonymous random site number, patient ID and date of the visits.

At the conclusion of the study, the completed signed and dated case report forms for the enrolled patients should be provided to the study data management center by the investigator for every patient enrolled in the study. Electronic signatures will be used in the case of an EDC system. A distinct case report form should be created for each unique instance when data is to be collected. ONLY data specified in the protocol should be collected and submitted to the study data management center. The investigator or staff under his/her supervision must complete the case report forms and neither AbbVie nor any agents acting on behalf of AbbVie may complete the case report forms.

### 10.0 Data Analysis Plan

#### 10.1 Overview:

The following sections provide a brief overview of the statistical methods used to address the study objectives. Detailed description of the statistical analyses, any deviation from the protocol and assumptions employed will be presented in the Statistical Analysis Plan that will be prepared prior to database close and initiation of any statistical analyses. In

addition the final sections describe particular considerations relevant to the observational nature of the current study.

#### 10.2 General Considerations:

Descriptive statistics consisting of the mean, median, standard deviation and 95% confidence interval of the mean for continuous scale variables and frequency distributions for categorical variables will be produced for the baseline characteristics. These descriptive statistics will be produced for the study cohort as a whole and for the three treatment cohorts as described in section 6.0.

Between cohort differences with respect to the baseline parameters will be assessed with the Chi-Square statistic for categorical variables and One Way Analysis of variance (ANOVA) for continuous scale variables. Variables for which a trend for statistical significance (P < 0.15) or clinically important difference (more than 2 - fold) are observed will be considered as potential confounders and will be included in the multivariate analyses or propensity score development described later. Descriptive statistics will be produced for all variables and the changes from baseline when Statistical Methods to Address the Study Objectives:

Between group differences with respect to achieving the primary effectiveness outcome, specifically a PGA of "0" or "1" at 24 months will be assessed with simple logistic regression analysis and multivariate logistic regression models adjusting for potential confounders or the propensity score. A more relevant analysis will be to assess the differences between the groups with respect to the time to achieving the end point. For this analysis Kaplan Meier based time to event (survival) analysis will be used with the log-rank test to assess the statistical significance of the between group differences. Cox's proportional hazards model will also be used to adjust for potential confounders or the propensity score.

Between groups differences with respect to the changes in the BSA, PGA, DLQI, Psoriasis

Related Pruritus Assessment VAS, Plaque Psoriasis and Psoriatic Arthritis Pain VAS, BDI,9SF-12 (second version) WLQ from baseline to 24 months of treatment will be assessed with One Way ANOVA or repeated measures, mixed effects general linear model adjusting for potential confounders or the propensity score. Planned contrasts will be used to assess between group differences at the other follow up time points. Pairwise between group comparisons will be adjusted for multiplicity with the Tukey's Least Significance Test.

In order to better assess the impact of the treatment received and changes in the regimen the treatment will be handled as a time – dependent covariate in these analyses.

With respect to achieving therapeutic response end points and incidence of articular and extra-articular manifestations between group differences will be assessed with multivariate logistic regression while Cox proportional hazard models will be used to assess between group differences with respect to the time of achieving therapeutic response and first occurrence of articular and extra-articular manifestations.

Descriptive statistics will be used to assess the between group and regional differences with respect to patient characteristics and disease parameters. Descriptive statistics will also be used to assess the practice patterns of Canadian dermatologists in the management of patients with moderate to severe PLAQUE PS. The study cohorts will be divided into Canadian regions as Quebec, Ontario, Maritimes and Western Canada.

Underdiagnosis of articular and extra articular manifestations will be assessed by the prevalence of existing articular manifestations and a survey of participating physicians with respect to their estimates of the prevalence of articular and extra- articular manifestations in the patients.

Safety will be assessed by the incidence of treatment emergent adverse events with adjusted relative risks used to compare the three treatment groups.

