# 5.2 Secondary Objectives:

- i. To compare the real life effectiveness of adalimumab to topical and traditional systemic agents in the prevention of development of articular and extra-articular manifestations in patients with moderate to severe Plaque PS.
- ii. To describe the profile and regional variation in terms of demographics, disease parameters, flare up trigger, comorbidities and concomitant medication use of Canadian patients with moderate to severe Plaque PS.
- iii. To describe the current practices and regional variation among Canadian dermatologists with respect to the screening and detection of articular manifestations indicating onset of PsA in patients with moderate to severe Plaque PS.

- iv. To describe the incidence of and risk factors for the development of articular and extra-articular manifestations in Canadian patients with moderate to severe Plaque PS.
- v. To describe the current population based burden of illness incorporating Health Care Utilization, Health Care Costs, Quality of Life, Psychological impact Work Productivity of moderate to severe Plaque PS in Canada.
- vi. To assess the impact of topical agents, traditional systemic agents and adalimumab on the Plaque PS related burden of illness incorporating Health Care Utilization, Health Care Costs, Quality of Life, Psychological impactWork Productivity in Canada.
- vii. To provide an ongoing assessment of the safety and tolerability of adalimumab, systemic and topical agents used in the management of moderate to severe Plaque PS in Canada.

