Effectiveness outcome measures will include changes in clinical outcomes and quality of life. Health economic assessments will be conducted to determine the impact of treatment on Psoriasis related burden of illness. The impact of Psoriasis and different treatments on work productivity will be assessed. The study will also identify prognostic factors for progression to Psoriatic Arthritis and treatment gaps in the detection and screening for articular and extra-articular manifestations. Regional differences within Canada with respect to the patient profile and the management of patients with Psoriasis will be described.

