### 2.3.2 Secondary

- 1. To compare the real-life effectiveness of adalimumab to topical and traditional systemic agents in the prevention of development of articular and extra-articular manifestations in patients with moderate to severe Plaque PS.
- 2. To describe the profile and regional variation in terms of demographics, disease parameters, flare-up trigger, comorbidities and concomitant medication use of Canadian patients with moderate to severe Plaque PS.
- 3. To describe the current practices and regional variation among Canadian dermatologists with respect to the screening and detection of articular manifestations indicating onset of PsA in patients with moderate to severe Plaque PS.
  - i. To describe the incidence of and risk factors for development of articular and extraarticular manifestations in Canadian patients with moderate to severe Plaque PS.
- 4. To describe the current population based burden of illness incorporation Health Care Utilization, Health Care Costs, Quality of life, Psychological Impairment, Work Productivity of moderate to severe Plaque PS.
  - To assess the impact of topical agents, traditional systemic agents and adalimumab on the Plaque PS related burden of illness incorporating Health Care Utilization, Health Care Costs, Quality of Life, Psychological Impairment, Work Productivity in Canada.
- 5. To provide an ongoing assessment of the safety and tolerability of adalimumab, systemic and topical agents used in the management of moderate to severe Plaque PS in Canada.

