## 3.11 Analysis of the Secondary Objectives

Between groups differences with respect to the changes in the BSA, PGA, DLQI, PASQ, BDI, SF-36 WLQ from baseline to 24 months of treatment will be assessed with One Way ANOVA or repeated measures, mixed effects general linear model adjusting for potential confounders or the propensity score. Planned contrasts will be used to assess between group differences at the other follow up time points. Pairwise between group comparisons will be adjusted for multiplicity with the Tukey's Least Significance Test.

In order to better assess the impact of the treatment received and changes in the regimen the treatment will be handled as a time-dependent covariate in these analyses. Descriptive statistics will be used to assess the between-group differences in healthcare resource utilization and healthcare costs associated with PS. With respect to achieving therapeutic response end points and incidence of articular and extra-articular manifestations between group differences will be assessed with multivariate logistic regression while Cox proportional hazard models will be used to assess between group differences with respect to the time of achieving therapeutic response and first occurrence of articular and extra-articular manifestations.

Descriptive statistics will be used to assess the regional differences with respect to baseline patient characteristics and disease parameters. Descriptive statistics will also be used to assess the practice patterns of Canadian dermatologists in the management of patients with

### COMPLETE - PS Statistical Analysis Plan Version 3.0 July 23rd, 2015 Page 31 of 231

moderate to severe Plaque PS. The study cohort will be divided into Canadian regions as Quebec, Ontario, Maritimes and Western Canada.

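### Objective iv promises risk factors for articular and extra-articular manifestations, but every model planned for these outcomes is a treatment contrast

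*Protocol*

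**What the plan says.** **The promise.** Protocol 5.2, objective iv, reads: "To describe the incidence of and risk factors for the development of articular and extra-articular manifestations in Canadian patients". SAP 2.3.2 carries it as sub-item i of objective 3: "To describe the incidence of and risk factors for development of articular and extraarticular manifestations in Canadian patients". Protocol 6.0 adds: "The study will also identify prognostic factors for progression to Psoriatic Arthritis". The rationale (Protocol 4.0) describes predictors of progression to psoriatic arthritis as unknown and presents the study as addressing that gap.

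**The planned models.** For the occurrence of these manifestations, Protocol 10.2 plans "incidence of articular and extra-articular manifestations between group differences will be assessed with multivariate logistic regression". For timing, the same sentence says "Cox proportional hazard models will be used to assess between group differences with respect to the time of achieving therapeutic response" and extends this to the first articular or extra-articular manifestation. SAP 3.11 repeats the sentence ("group differences will be assessed with multivariate logistic regression while Cox") and adds no further model for the outcome.

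**The covariate rule.** Protocol 10.2 compares baseline variables between the three cohorts. "Variables for which a trend for statistical significance (P < 0.15) or clinically important difference (more than 2 - fold) are observed" are treated as potential confounders and go into the multivariable models or into a propensity score. SAP 3.8 keeps the same thresholds. SAP 3.2 lists covariate adjustment, propensity scores and stratification as options, to be chosen from the data.

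**The concern.** A risk-factor analysis asks which patient characteristics predict the outcome. A treatment-contrast model asks whether outcomes differ by cohort after adjustment for confounding. The second does not deliver the first, because its covariates are chosen for a different purpose. The screen here asks whether a variable is related to which treatment was prescribed. It never asks whether the variable is related to joint or extra-articular disease.

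A strong predictor that plays no part in prescribing would usually not be picked up, while a variable that drives prescribing but does not predict the outcome would be. Without a separate model, the report must either leave half of a stated objective unaddressed or build an unplanned model after the data are seen.

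**Working it through.** Neither document gives a sample size, event count or power for objective iv, so there is no figure to reproduce. The check traces the objective through the plan and then calculates what the covariate screen selects.

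**1. Trace**

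| Place | What it gives for these manifestations |
|---|---|
| Protocol 5.2 iv and 6.0; SAP 2.3.2 | Incidence and risk or prognostic factors are promised |
| Protocol 10.2; SAP 3.11 | Logistic and Cox models, both for between-group differences |
| Protocol 10.2, underdiagnosis paragraph | Prevalence of existing manifestations and a physician survey; no predictors |
| Protocol 10.2; SAP 3.8, 3.9, 3.11 | Descriptive summaries, with breakdowns by cohort and region but not by whether a manifestation developed |
| SAP list of tables | Model tables for PGA, DLQI and burden of illness; joint and PASQ data only by visit (Tables 18 to 20) |

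No section names candidate risk factors or tests baseline variables against the manifestation outcome.

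**2. What the screen selects**

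Inputs from the documents:
- Cohorts of 330:165:165 (Protocol 10.3, SAP 2.7).
- Attrition of 25%: 0.75 × 330 = 247.5 and 0.75 × 165 = 123.75, rounded to 248:124:124, total 496.
- Entry if P < 0.15 or the difference is more than 2-fold.

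Assumptions: a binary factor with the same true prevalence in every cohort, between 5% and 50%. The 2-fold clause is read as the largest observed cohort proportion exceeding twice the smallest.

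Statistic: X² = Σ nᵢ(p̂ᵢ − p̄)² / [p̄(1 − p̄)] on 2 degrees of freedom. The factor enters if X² > −2 ln(0.15) = 3.79. A truly balanced factor passes the P-value clause with probability about 0.15 by definition. Simulation with 20,000 replicates per row adds the 2-fold clause:

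| Cohorts | Prevalence | P < 0.15 alone | P < 0.15 or > 2-fold |
|---|---|---|---|
| 330:165:165 | 5% | 0.153 | 0.257 |
| 330:165:165 | 10% | 0.151 | 0.153 |
| 330:165:165 | 20% to 50% | 0.149 to 0.154 | 0.149 to 0.154 |
| 248:124:124 | 5% | 0.151 | 0.341 |
| 248:124:124 | 10% | 0.148 | 0.170 |
| 248:124:124 | 20% to 50% | 0.150 to 0.153 | 0.150 to 0.153 |

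A balanced factor of 10% to 50% prevalence is therefore selected with probability about 0.15 to 0.17, and is not selected 83% to 85% of the time. For a rare factor, chance 2-fold differences raise selection to 0.26, or 0.34 after attrition.

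**3. A factor related to prescribing**

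Assume 35% prevalence in the adalimumab cohort and 30% in the other two. Then p̄ = 0.5 × 0.35 + 0.5 × 0.30 = 0.325, and each cohort deviates from it by 0.025. The non-centrality is 660 × 0.025² / (0.325 × 0.675) = 0.4125 / 0.2194 = 1.88, which gives an entry probability of 0.40. The strength of the factor's association with joint disease appears nowhere in this calculation.

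**4. The propensity-score option**

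If selected variables go into a propensity score, the outcome model contains treatment and the score. No factor then has its own odds ratio or hazard ratio, so the entry probabilities above no longer matter.

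**The case against.** Several points on the other side are fair.

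- **The screen bars nothing.** It is an inclusion rule for confounders. A reader might infer that balanced risk factors are excluded by rule, but no sentence forbids adding other variables. They are simply not selected by the only rule stated.
- **No misuse is announced.** A reader might infer that coefficients from the treatment models will be reported as risk factors. Neither document says so, and the screen is presented only as control of confounding.
- **The objective is worded as description.** That weakens the demand for formal testing. It does not fill the gap, because no description by manifestation status is planned either.
- **The list of tables is weak evidence.** It also shows no adverse-event table, although safety analyses are planned, and no table for the planned manifestation contrast. Absence from it does not show that an analysis is not intended. The point rests on the text of Protocol 10.2 and SAP 3.11.
- **Many plausible candidates will not be balanced.** Treatment follows physician judgment, and the reimbursement conditions in Protocol 3.0 are tied to severity and body surface involvement. BSA and PGA could well enter. The 15% applies to balanced factors only.

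What remains after these points is that no analysis is specified for the risk-factor part of the objective, and the nearest available model selects its covariates for another purpose.

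**Conclusion.** The risk-factor part of objective iv is not answered by the analyses as planned. This follows from the text of both documents and needs no assumed number. The selection figures (about 15% for a common balanced factor, about 26% at 5% prevalence with 660 patients) show how poorly the screen would serve as a risk-factor search. They depend on assumed prevalences and exact balance.

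Two stronger conclusions are tempting. One is that the study cannot answer the objective. The documents do not support this, since most of the baseline variables needed are already in Table 1. The other is a power figure for detecting a risk factor. The documents give no 24-month incidence, hazard ratio or factor prevalence for these outcomes. The figure of about 30% in Protocol 4.0 concerns psoriasis patients who develop psoriatic arthritis. It is neither a baseline prevalence nor a 24-month rate, and it does not cover extra-articular events.

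This is a cheap improvement to a secondary objective. The primary PGA comparison is unaffected.

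**What to change.** Add to Protocol 10.2 and SAP 3.11 a separate exploratory analysis for objective iv, fixed before the outcome data are examined:

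1. **Outcomes.** Model first articular and, separately, first extra-articular manifestation with a Cox or discrete-time model. Define each event and its data source.
2. **At-risk set.** Include patients without that manifestation at baseline, and state how this is established. Table 1 records baseline concomitant psoriatic arthritis only where routine care provides it, so a rule for unknown status is needed.
3. **Candidates.** Enter a short list from Table 1 regardless of cohort imbalance: for example age, sex, smoking, weight, disease duration, family history of psoriasis, BSA, PGA and treatment cohort. At one parameter each for the first eight, plus two for the three cohorts, this is 10 parameters. Use baseline PASQ only if PASQ does not also define the event, since it records self-reported joint pain and swelling.
4. **Fitting.** Use a penalised fit (ridge or Firth) if events are sparse relative to the parameters.
5. **Reporting.** Give estimates with confidence intervals, labelled exploratory, in one added table. State that coefficients from the treatment-contrast models will not be reported as risk factors.

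The cost is one SAP paragraph, one analysis and one table, using variables already in the schedule. The downside is wide intervals if few events occur and some uncertainty about who was at risk at baseline.

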# 5.3.2 Secondary Endpoints:

The following secondary endpoints will be assessed:

- i. Time to achieving  $\underline{PGA} \le 1$  over 24 months of follow up.
- ii. Percent of patients with  $\underline{PGA} \le 1$  at 3, 12, 18 and 24 months
- iii. Signs and symptoms suggesting onset of PsA:
  - i. Change in the modified Psoriasis and Arthritis Screening Questionnaire (PASQ). This is an 11 item tool that ascertains self reported presence of joint pain and swelling. This will be assessed at 3, 6, 12, 18 and 24

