| Dose                                                      | X     |    |    |    |    |    |
| Duration                                                  |       |    |    |    |    |    |
| Reason for discontinuation                                |       |    |    |    |    |    |
| Concomitant Medications (Emphasis on Psoriasis Treatment) | X     | X  | X  | X  | X  | X  |
| Concomitant Psoriatic Arthritis                           | X2    |    |    |    |    |    |
| Rheumatoid Factor                                         | X2    |    |    |    |    |    |
| C - Reactive Protein or hs- CRP                    | X2    | X2 | X2 | X2 | X2 | X2 |
| Erythrocyte Sedimentation Rate (ESR)                      | X2    | X2 | X2 | X2 | X2 | X2 |
| Clinical Laboratory Tests                                 | X2    | X2 | X2 | X2 | X2 | X2 |

|                                                                    | Month |    |    |    |    |    |
|--------------------------------------------------------------------|-------|----|----|----|----|----|
| Variable                                                           | 0     | 3  | 6  | 12 | 18 | 24 |
| Visit Number                                                       | 1     | 2  | 3  | 4  | 5  | 6  |
| Body Surface Area (BSA)                                            | X     |    | X  | X  | X  | X  |
| Psoriasis and Arthritis Screening Questionnaire (PASQ)             | X     | X  | X  | X  | X  | X  |
| Use of Phototherapy                                                | X     | X  | X  | X  | X  | X  |
| Physician's Global Assessment of Disease Activity (6 Point Likert) | X     | X  | X  | X  | X  | X  |
| Patient's Global Assessment of Disease Activity (VAS)              | X3    | X3 | X3 | X3 | X3 | X3 |
| Dermatology Life Quality Index                                     | X3    | X3 | X3 | X3 | X3 | X3 |
| Medical Outcomes Study – Short Form 12                             | X3    |    | X3 | X3 |    | X3 |
| Health Care Utilization Questionnaire                              | X3    |    | X3 | X3 |    | X3 |
| Beck Depression Inventory                                          | X3    |    | X3 | X3 |    | X3 |
| Work Limitations Questionnaire                                     |       |    | X3 | X3 |    | X3 |
| Rheumatology Consult4                                              | X     | X  | X  | X  | X  | X  |

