| Compliance assessment                                              |       | X  | X  | X  | X  | X  |

- 1. Only changes from previous visit will be recorded
- 2. Only if used as part of routine care. For the baseline visit, historical data up to 6 months could be used.
- 3. Self Administered questionnaires. These could be completed at the physician's office, at home and sent by mail.
- 4. Relevant sections of the Case Report Form to be completed by rheumatologists or information must be obtained from the rheumatologists.

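### Under-diagnosis of joint disease is to be judged from a prevalence of undefined source and physicians' own estimates, with no patient-level link, and the SAP carries no such analysis

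*Protocol*

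**What the plan says.** Protocol 6.0 says the study will identify "treatment gaps in the detection and screening for articular and extra-articular manifestations". Secondary objective iii (Protocol 5.2) is to describe how dermatologists screen for and detect articular manifestations, with regional variation. The method is one sentence in Protocol 10.2: "Underdiagnosis of articular and extra articular manifestations will be assessed by the prevalence of existing articular manifestations and a survey of participating physicians", the survey being "with respect to their estimates of the prevalence of articular and extra- articular manifestations in the patients".

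Protocol Table 1 schedules three items that bear on this:

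- "Concomitant Psoriatic Arthritis", at month 0 only, under footnote 2: "Only if used as part of routine care".
- The PASQ, at month 0 and every later visit. Protocol 5.3.2 describes it: "This is an 11 item tool that ascertains self reported presence of joint pain and swelling".
- A rheumatology consult row, at every visit.

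The SAP keeps the objective (2.3.2, item 3) and the aim on detection gaps (2.4). It summarises concomitant PsA (3.8.2), describes PASQ and rheumatology consult at follow-up (3.9), and compares PASQ change between treatment groups (3.11). The nearest SAP text on physician behaviour is "Descriptive statistics will also be used to assess the practice patterns of Canadian dermatologists". Under-diagnosis and the physician survey appear in neither the SAP methods nor the titles in its List of Tables.

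**The concern.** To measure under-diagnosis, one needs something that does not depend on the diagnosis having been made, compared with the diagnosis in the same patients. The planned sentence secures neither. One component has no stated source. The other is the opinion of the physicians whose detection is in question. Good agreement between the two could therefore be reported as evidence of adequate detection when it carries no information about missed cases.

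Protocol 4.0 itself names a gap in screening and detection as part of the rationale, so readers will look for an answer. Better data are already being collected but are not brought together. Because the SAP omits the analysis without comment, the aim may also go unreported, or be addressed by a method chosen after the data are seen.

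**Working it through.** **1. Two readings of existing articular manifestations.** The documents give no figure for under-diagnosis (no target, precision or PASQ cut-off), so there is nothing to reproduce. The check starts from the text.

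| Reading | First figure | Second figure | What the comparison can show |
|---|---|---|---|
| Recorded PsA item (Table 1, footnote 2) | Share with a recorded diagnosis | Physicians' estimate | Both can omit the same missed patients |
| PASQ at month 0 | Share who screen positive | Physicians' estimate | A group-level difference; not which patients lack a diagnosis |

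Neither document says which is meant.

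**2. Illustration of the first reading.** Inputs: N = 660 (Protocol 6.2); true baseline prevalence 30%, assumed (Protocol 4.0 gives about 30% as the share who develop PsA, which is not a baseline prevalence); detection d of 50%, 70% or 90%, assumed; physicians' estimates equal to recorded diagnoses, assumed.

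- True cases = 660 × 0.30 = 198.
- Recorded prevalence = 0.30 × d.
- Missed = 198 × (1 − d).

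| d | Recorded prevalence | Missed | Planned gap |
|---|---|---|---|
| 50% | 15% | 99 | 0 |
| 70% | 21% | 59 | 0 |
| 90% | 27% | 20 | 0 |

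The zero gap follows from the last assumption. The table shows only that, under this reading, the two planned figures need not separate these situations.

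**3. What a month-0 cross-tabulation would add.** The documents give no PASQ accuracy, so assume sensitivity = specificity = a, from 0.7 to 0.9, with detection unrelated to the PASQ result among true cases. There are 660 − 198 = 462 patients without PsA.

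- PASQ-positive, all = 198a + 462(1 − a): 277 at a = 0.7 and 224 at a = 0.9.
- PASQ-positive without recorded PsA = 198(1 − d)a + 462(1 − a).
- Share = second ÷ first; 95% half-width = 1.96 × √[share × (1 − share) ÷ first].

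| d | a = 0.7 | a = 0.9 |
|---|---|---|
| 50% | 208/277 = 75% | 135/224 = 60% |
| 70% | 180/277 = 65% | 100/224 = 44% |
| 90% | 152/277 = 55% | 64/224 = 29% |
| 100% | 139/277 = 50% | 46/224 = 21% |

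Half-widths are about 5 to 7 points. At a given PASQ accuracy the share moves with detection, which the planned gap in step 2 does not. It does not fall to zero when nothing is missed: at d = 100% all 46 to 139 such patients are false positives. At d = 50% it captures only 69 (99 × 0.7) to 89 (99 × 0.9) of the 99 missed cases. It is informative, but it is not a count of missed disease.

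**4. SAP coverage.** PsA status, PASQ and rheumatology consult are summarised separately (3.8.2, 3.9; Tables 10–15, 19, 20 and 60, with a joint diagram score in Table 18). No title crosses PASQ with recorded PsA. Protocol 10.1 says the SAP will set out deviations from the protocol; none is stated here. The mock-table bodies are not in the text available, so this rests on the methods text and the titles.

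**The case against.** The strongest reply is that the protocol speaks of manifestations and not of diagnosed PsA, and that its own endpoint for signs of PsA onset is the PASQ, a patient self-report. On that reading, measured symptoms are set against physicians' beliefs, which is a coherent group-level check. This stands as a possible reading, and it is why the blind spot is stated as conditional. It does not supply the missing definition or a patient-level link.

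Ascertainment is also wider than one row. The month-0 physical examination and comorbidity rows do not carry footnote 2, and Protocol 6.5.1 asks for a complete baseline examination and history. That weakens any claim that only routine-care data exist, but neither source is tied to under-diagnosis.

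The SAP's summary of concomitant PsA may preserve the prevalence half of the method. That is fair; what is absent is the survey and any comparison. The survey's absence from Table 1 and the case report form sections proves little, because those list patient data.

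A reader might infer that a missed patient is necessarily in neither figure, or that half the cases will go undetected unseen. The documents do not support this. The source is undefined, physicians may allow for undetected cases when estimating, and the detection rates above are assumptions. Nor would PASQ-positive patients without a diagnosis form an upper bound, since false negatives fall outside them. Cases confirmed at a later consult would not form a lower bound, since they can include onset after month 0 and depend on who was referred.

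Finally, under-diagnosis is not itself a listed objective or endpoint. That limits the weight of the point, but Protocol 6.0 and objective iii, both carried into the SAP, still call for an account of detection.

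**Conclusion.** The point holds in conditional form. Protocol 10.2 leaves the source of existing manifestations undefined and compares group figures only. If the source is the recorded PsA item, missed patients can be absent from both figures; if it is the PASQ, undiagnosed patients still cannot be identified. Under either reading, the SAP's methods and table titles omit the analysis and the survey without a stated reason, while keeping the objective.

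The size is not known. The 99 and 59 missed patients are illustrations that rest on 30% baseline prevalence, 50% or 70% detection, and estimates equal to recorded diagnoses. The change should be made because it costs one table and replaces a weak method with a better one. It concerns a secondary descriptive aim and leaves the primary PGA comparison untouched.

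**What to change.** In Protocol 10.2 and SAP 3.11:

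1. State the source of existing articular manifestations.
2. Add one month-0 table of PASQ result, with the cut-off fixed beforehand, by recorded PsA status. Separate assessed and absent from not assessed, because footnote 2 makes a blank ambiguous.
3. Report the share of PASQ-positive patients without recorded PsA, overall and by the four regions, with 95% confidence intervals. Show the month-0 rheumatology consult result where available.
4. Label it as screen-positive without a recorded diagnosis, subject to false positives and false negatives, and not as an upper or lower bound. Note that the baseline questionnaires are completed at the physician's office (Protocol 6.5.1), so PASQ answers may influence the PsA entry.
5. State that extra-articular under-diagnosis is not measured by this table.
6. Restore the physician survey as context, or record its removal as a deviation.

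The cost is SAP and protocol wording, a pre-set cut-off and one cross-tabulation of data already scheduled. Restoring the survey would add some conduct work; recording its removal would not. The downside is that the PASQ is a screen, so the figure is approximate, and regional intervals will be wider than the overall one.
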